- Alcohol usage in the past 60 days prior to assessment specifically and the pattern of chronic usage.
- Review inclusion and exclusion criteria
- Collection of blood for hematology, coagulation, clinical chemistry to include amylase and lipase, ammonia, and in female patients, a pregnancy test.

- Physical examination, including height, weight (body mass index will be calculated based on these variables), and vital signs (systolic and diastolic blood pressure, pulse rate, respiratory rate and body temperature)
- Ultrasound or cross –sectional imaging of the abdomen. This is standard of care in patients hospitalized with alcoholic hepatitis.

Study treatment:

Patients will be randomized to receive 28 days of methylprednisolone 32 mg daily OR therapy that includes a combination of anakinra (interleukin-1 receptor antagonist, IL-1 RA) 100mg by subcutaneous injection daily for 14 days plus pentoxifylline 400 mg orally three times daily for one month PLUS zinc supplements (220 mg of zinc sulfate) given orally for 6 months.

Assessments at baseline and during study treatment:

Study day 0 – baseline (within 48 hours of study enrollment)

- Complete collection of all baseline history. Review of alcohol use history.
- Complete collection of all indicated standard of care laboratory evaluations (chemistry, hematology, coagulation, urine, microbiology, viral, and TB testing) .
- Ascites evaluation, if present.
- Collection of baseline research testing to include urine, blood, DNA and stool testing.
- Collect prior and concomitant medications.
- Clinical assessment to include vital signs and physical exam details.
- Nutritional assessment with a hand grip dynamometer

Treatment day 1 – time zero (alternatively note this as treatment day one with no time and above as study day 1 baseline)

- Begin continuous AE review and reporting
- Begin subcutaneous injected study medication or placebo injection
- Begin dosing of oral study medications (pentoxifylline 400 mg 3 times daily PLUS zinc sulfate 220 mg once daily)/placebo or oral methylprednisolone/placebo preparation

Treatment day 2:

- Inpatient assessment to include:
 - Review baseline history for changes. Review alcohol intake history.
 - Collection of prior and concomitant medications
 - Clinical assessment including vital signs and physical exam details
 - Collection of blood for clinically indicated laboratory studies.
 - Collection of research laboratory studies including urine and blood.

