 - Review baseline history for changes. Review alcohol intake history.
 - Collection of prior and concomitant medications
 - Clinical assessment including vital signs and physical exam details
 - Collection of blood for clinically indicated laboratory studies.
- **STOP** subcutaneous injection of study drugs or placebo injection.
- Continue oral study medications (pentoxifylline 400 mg 3 times daily PLUS zinc sulfate 220 mg once daily)/placebo or oral methylprednisolone/placebo preparation.
- Continuous AE review and reporting.

Treatment days 16-27:

- If patient remains inpatient or has a clinically indicated outpatient visit:
 - Review baseline history for changes. Review alcohol intake history.
 - Collection of prior and concomitant medications
 - Clinical assessment including vital signs and physical exam details
 - Collection of blood for clinically indicated laboratory studies.
- Continue oral study medications (pentoxifylline 400 mg 3 times daily PLUS zinc sulfate 220 mg once daily)/placebo or oral methylprednisolone/placebo preparation.
- Continuous AE review and reporting.

Treatment day 28 ± 2 days:

- Inpatient assessment or **required** outpatient clinic visit to include:
 - Review baseline history for changes. Review alcohol intake history.
 - Collection of prior and concomitant medications
 - Clinical assessment including vital signs and physical exam details
 - Collection of blood for clinically indicated laboratory studies.
 - Collection of research laboratory studies including urine and blood.
- Continue oral study medications (pentoxifylline 400 mg 3 times daily PLUS zinc sulfate 220 mg once daily)/placebo or oral methylprednisolone/placebo preparation.
- Continuous AE review and reporting.

- Nutritional assessment with a hand grip dynamometer

Treatment day 29:

- **STOP** dosing of oral study drug or oral methylprednisolone preparation
- **Continue** once daily dosing of oral zinc supplement or oral placebo preparation
- Continuous AE review and reporting.

Treatment days 29 to 2 months ± 2 weeks:

- Continue once daily dosing of oral zinc supplement or oral placebo preparation
- Continuous AE review and reporting.
- If patient remains inpatient at treatment month 2 or completes clinically indicated outpatient visit at treatment month 2:
 - Review baseline history for changes. Review alcohol intake history.
 - Collection of prior and concomitant medications
 - Clinical assessment including vital signs and physical exam details

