Standard	Clinical assessment	x	x	x	x	x	x	x	x	x	x
	Alcohol intake	x	x	x	x	x	x	x	x	x	x
	Liver panel (bilirubin, alkaline phosphatase, AST, ALT) and GGT	x	x	x	x	x	x	x	x	x	x
	Serum electrolytes, creatinine, BUN	x	x	x	x	x	x	x	x	x	x
	Serum albumin, total protein	x	x	x	x	x	x	x	x	x	x
	Prothrombin time, INR	x	x	x	x	x	x	x	x	x	x
	Complete blood count	x	x	x	x	x	x	x	x	x	x
	Haptoglobin	x									x
	Lipid panel	x									x
	Amylase, lipase	x									
	HIV	x									
	HAV Ab, HBsAg, HBcore Ab (total)	x									
	HCV Ab	x									
	PPD	x									
	Blood cultures x2	x									
	Urine culture & urinalysis	x									
	24 hour urine (Na, K, creatinine, protein)	x									
	Urine toxicology	x									
	Ascites for albumin, total protein, cell count and differential (if present)	x									
	Ascites culture	x									
	Stool studies (if diarrhea): C. difficile, culture	x									
	Complete abdominal ultrasound or cross-sectional radiology	x									x
Research	Gut permeability studies	x ‡				x		x			x
	Serum zinc, urine zinc	x				x		x			x
	Stool (DNA microbiome)	x						x			x
	Urine (KIM-1)	x	x day2	x		x		x			x
	Biomarkers = Cytokines	x	x day2	x		x		x			x

	DNA = Pharmacogenomics	x									
	Serum micro RNA	x		x		x		x			x
	Monocyte prep (U Mass, U Louisville)	x		x							x
Blood	Research total volume = 179 mL	45		30		37		30			37
	SOC total volume = 208 mL	82	14	14	14	14	14	14	14	14	14
	Combined = 387 mL = 26 tbspns	117	14	44	14	51	14	44	14	14	51

- * clinically indicated; †± 2 weeks ‡ within first 28 days for non-ICU patients

Sub-Study Procedures

1. Optional Natural History (minimal risk with urine and blood collection): All screened subjects meeting inclusion and exclusion criteria below or declining consent to randomization will be invited to join this study of the natural history of severe acute alcoholic hepatitis. The natural history of patients with severe alcoholic hepatitis is not well documented in the current era. Prospective collection of data in parallel with the randomized study subjects has great potential value. Every patient who agrees and gives consent will be seen in follow-up as clinically indicated. At each visit that coincides with collection of samples for research, or as close as possible to Baseline, Day 7, Day 28, Month 3 and Month 6, the subjects will be offered the opportunity to participate. Patients may also be asked to participate in the natural history study as a one-time draw at the day of consent.

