Blood for research purposes will be collected at the same time as blood for clinical care. Urine specimens will be collected either with clinical care samples or at special research visits during follow-up after discharge. All samples will only be identified using a unique study number and processed as necessary for local storage or shipping to central testing sites.

Stool samples will be collected by giving a collection kit to the subjects.

A unique study number will be assigned to each subject. The unique study number will be assigned

centrally at the time of randomization and used to code all samples. The study site will be identified by the first digit (1 – 4), the subject by the last 3 digits and the disease stratification by the total number of digits (4 for moderate alcoholic hepatitis). This procedure allows any site to exceed 100 subjects enrolled in either study.

Data: Any past medical history, family history, social history (including dietary and occupational history), medications and other ingested supplements potentially related to etiology or complications of liver disease and alcohol consumption not provided in the electronic medical records.

Electronic medical record: Data pertaining to current hospitalization, past medical history, family history, social history (including dietary and occupational history), medications and other ingested supplements potentially related to etiology or complications of liver disease and alcohol consumption; physical examination.

Standard of care laboratory investigations: Results of routine blood chemistry tests = blood electrolytes, renal and liver function tests, pancreas enzymes, lipid panel, urine and fluid chemistry; hematology = complete blood count, coagulation and hemolysis studies, fluid cell counts; infectious diseases = viral hepatitis serologies, tests for HIV and tuberculosis; blood, urine and fluid cultures; stool culture and toxins. Results of routine radiology = chest x-ray, complete abdominal ultrasound.

Data from the results of research studies: gut permeability, blood and urine zinc, blood DNA (genomics) and stool DNA (microbiome), blood micro RNA, blood and urine inflammation biomarkers, blood mononuclear cells responses.

A measure of nutritional status will be obtained via a hand grip measurement with the JAMAR dynamometer.

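### A footnote on the Day 0 gut-permeability sample, on its most natural reading, lets a value drawn on treatment serve as baseline, and no analysis rule prevents it

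*Combined protocol and SAP*

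**What the plan says.** The schedule of events in section 6 plans gut-permeability studies at Day 0, Day 28, 3 months and 6 months. Only the Day 0 cell is marked with a double dagger, which the footnote defines as "within first 28 days for non-ICU patients". Eight research rows have a Day 0 sample: permeability, zinc, stool, KIM-1, cytokines, DNA, micro RNA and the monocyte preparation. The other seven, including "Serum zinc, urine zinc", carry no such window.

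The visit text in section 6 sets Study day 0 within 48 hours of enrollment and lists there: "Collection of baseline research testing to include urine, blood, DNA and stool testing". Permeability is not named. Treatment day 1 follows, with the instruction "Begin subcutaneous injected study medication or placebo injection" and the start of the oral drugs, zinc included. The first follow-up visit with a permeability sample is "Treatment day 28 ± 2 days".

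Sections 1 and 3 list change in gut permeability as a secondary outcome, and section 3 says it is measured by serum tests. Section 2 gives improvement of permeability as the purpose of zinc. Section 13 sets out the MELD analyses for the moderate trial, the log-rank and Cox analyses for the severe trial, and a general plan for fold-change outcomes. It does not define a permeability baseline or say how a first sample drawn after dosing is handled.

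**The concern.** A change score estimates a treatment effect cleanly when its starting value predates treatment. Read as a sampling window, the footnote allows the starting value to be drawn after up to about four weeks of randomised therapy. One arm's regimen contains zinc from day 1, and zinc is there to act on this very measure. If the arms have already separated when a late sample is drawn, subtracting that sample removes part of the difference the outcome is meant to show. At the extreme, the baseline and the first follow-up sample could be the same draw, giving a change of zero.

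What is at stake is one mechanistic secondary outcome. It bears directly on the trial's hypothesis about gut barrier function, but it carries no power claim.

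**Working it through.** The documents give no permeability effect size, variance or sample-size figure, so there is no stated number to reproduce. The check is one of timing, followed by an illustration under stated assumptions.

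**1. Window against dosing.** Inputs: the footnote window (days 0-28) and the dosing start (treatment day 1), on one day count. Days 0 to 28 are 29 calendar days. Days 1 to 28, that is 28 of the 29, fall on or after the start of dosing.

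**2. Window against the first follow-up visit.** Day 28 ± 2 covers days 26-30. The overlap with days 0-28 is days 26, 27 and 28. The event that starts the 28 days is not defined, so a second case is needed. Assume dosing starts k = 0 to 2 days after the clock starts, and the window closes 27 or 28 days after the clock starts. It then closes on treatment day 28 − k or 29 − k, that is between day 26 and day 29, and the overlap is 1 to 4 days.

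**3. Effect on the difference in change.** Let f(t) be the between-arm difference at day t as a fraction of its maximum, with f(0) = 0. Let s be the share of baselines drawn late (assumed equal in the two arms), and T the late draw day (assumed uniform over 0-28).

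Observed difference in change at day d = f(d) − s × E[f(T)]

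Proportional shrinkage = s × E[f(T)] / f(d)

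*Early, sustained separation:* f(t) = min(t/28, 1). E[f(T)] = 14/28 = 0.5, and f(28) = f(90) = f(180) = 1.
- s = 0.25: 0.25 × 0.5 = 12.5% at all three times.
- s = 0.50: 0.50 × 0.5 = 25% at all three times.

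*Slow separation over six months:* f(t) = t/180. E[f(T)] = 14/180, so E[f(T)]/f(d) is 14/28 = 0.50, 14/90 = 0.156 and 14/180 = 0.078.

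| s | Day 28 | Day 90 | Day 180 |
|---|---|---|---|
| 0.25 | 12.5% | 3.9% | 1.9% |
| 0.50 | 25% | 7.8% | 3.9% |

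*Few late draws:* s = 0.05 under early separation gives 0.05 × 0.5 = 2.5%.

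*No difference in the first 28 days:* E[f(T)] = 0, so there is no bias for any s.

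The shares and shapes are all assumptions; the documents supply neither.

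**The case against.** The strongest reply is that the footnote may be an ICU exemption: during the first 28 days, do the test only in patients who are not in the ICU. That reading is possible but fits poorly. The mark sits on the Day 0 cell alone, where a reference to the first 28 days would have little to govern, and the Day 28 cell is unmarked.

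Other text points towards a Day 0 draw. Section 7 says "Blood for research purposes will be collected at the same time as blood for clinical care", and the outcome is a serum measure. The table's research blood volumes (45 + 30 + 37 + 30 + 37 = 179 mL) place nothing in the Day 8-27 column. This makes it unsafe to infer that late baselines are planned, but it does not rule them out. The volumes are weak evidence, because they also show nothing for the Day 2 cytokine sample.

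It is also fair to say that the two places do not flatly contradict each other, since the Day 0 visit text does not name permeability. The footnote may be a deliberate feasibility exception. An exception would still need a defined start and an analysis rule, and neither is given.

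A reader might go further in three ways that the documents do not support:
- *That any post-dose baseline is biased.* It is not, unless the arms already differ at the draw.
- *That an early difference could wane and the comparison change sign.* On day 29 the plan stops "dosing of oral study drug or oral methylprednisolone preparation", but zinc, the component tied to permeability, continues to 6 months. Nothing ties waning to the drugs that stop.
- *That late sampling selects patients on ICU status affected by treatment.* That assumes status is judged at the draw, which the footnote does not say.

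**Conclusion.** The point holds as a gap in timing and definition. On the most natural reading of the footnote, an on-treatment permeability value, even one overlapping the Day 28 visit, can stand as baseline for a named secondary outcome, and nothing in section 13 prevents it.

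The consequence is conditional. If the arms differ at the late draw, the difference in change is biased. Under early, sustained separation it is attenuated, by 12.5% or 25% in the illustration with a quarter or half of baselines late. Under slow separation, the loss at day 180 is 1.9% or 3.9%. With no early effect it is nil. The true size cannot be estimated, because neither the share of late draws nor the course of the effect is given.

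The 6-month mortality outcome and comparisons of on-treatment levels that use no baseline are untouched. The lack of a permeability-specific model in section 13 is a separate matter and is not caused by this footnote. The correction is worth making because it is cheap, not because the trial's main conclusion depends on it.

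**What to change.** 1. Reconcile the footnote with the Study day 0 text so that the permeability sample is drawn before the first dose, with the Day 0 research blood, wherever feasible.
2. If a window is kept, state the event that starts it and what applies to ICU patients.
3. In the analysis plan, count only samples drawn before the first dose as baseline. Treat a later first sample as an on-treatment value at its actual draw time.
4. Report by arm how many patients have a pre-dose sample.

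The cost is a footnote clarification and a short analysis rule that compares draw time with first dose. No assay is named, so it is an assumption that the test needs only a simple Day 0 blood draw. The downside is that some patients, in a number the documents do not allow one to predict, will have no baseline value for this secondary outcome.

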The potential benefits to every subject participating in the clinical trial are related to receiving optimal patient-centered care for their condition. This includes ensuring the mobilization of available resources for rehabilitation programs and the education of all involved patients and their families on the possible consequences of alcohol consumption, particularly in high risk sub- populations. While ideally occurring in the care of all patients with alcoholic hepatitis, the study team will provide patients with the personal healthcare navigation assistance that is not available to every individual.

There may be immediate additional benefits to those in the active study arms if the outcomes are favorable. If the outcomes are favorable, all patients with severe alcoholic hepatitis may benefit from extrapolation of the findings. If the outcomes are negative, other subjects will be protected from the risks of treatment that has no additional benefit to convey.

There is a potential societal benefit in the general outcomes of the clinical trial with respect to alcohol consumption, alcoholism and alcoholic liver disease. In addition, the potential financial benefits of a successful program are substantial.

13. Biostatistics:

Sample size for study of patients with moderate acute alcoholic hepatitis

To compare change from baseline in the two groups of moderate AAH patients, we find that a two-sided two sample t-test of change in MELD score from baseline (mean=17.0) to 30 days with an overall sample size of 108 patients (54 in each treatment group) achieves 80% power with an alpha level of 0.05 to detect a difference in mean change of MELD score of 5.0 in the control group compared to a mean change of 8.0 in the intervention (probiotic) group with a common estimated group MELD score standard deviation of 5.559.

Adjusting for a total of 20% withdrawal, lost to follow-up or non-evaluable, we have $n^* = 108 / (1 - 0.20) = 108 / 0.80 = 136$ patients total or 68 patients in each treatment group. We expect that, in a multivariate model, we will have the power to detect smaller treatment group differences due to the partition of the variance among the predictors.

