Statistical analysis plan: Our primary analysis of change in MELD score from baseline to 30 days will be an unadjusted comparison of change (Day 30 – Baseline) using a standard two- group t-test at a two-sided alpha level of 0.05 with appropriate adjustment for unequal variances. We will also conduct secondary analyses to further investigate factors that influence the change as well as adjust for any imbalances in patient characteristics and covariates between treatment groups. Our initial model will be an Analysis of Covariance (ANCOVA) model with change in MELD score as the outcome and with treatment group (0=control, 1=probiotic) and baseline MELD score as predictors. Additional models will include patient characteristics such as age, gender, time since diagnosis as well as other covariates such as ALT, AST, and other laboratory measures at baseline. Finally, as it is likely that MELD score can be calculated throughout the duration of the study, we will use mixed models to analyze the longitudinal MELD score data. Mixed (random effects) models are used to adjust for the inherent correlation among the laboratory (and, thus, MELD score) measures on the same patient. We will consider treatment as a fixed effect, but most other factors as random effects. The model will also include a time metric, so that, rather than the change from baseline, we can use the coefficients of the times as estimates of the change from baseline (time=0), adjusted for the other factors in the model. So, for example, if MELD score is calculated at Days 0, 7, 14, 21, and 30, the model might look like: $MELDt = \beta_0 + \beta_1*tx + \beta_2*gender + \beta_3*age + \beta_4*Day7 + \beta_5*Day14 + \beta_6*Day21 + \beta_7*Day30$ where $MELDt$ = MELD score at time t ($t=0, 7, 14, 21, 30$), $\beta_0 \dots \beta_7$ = regression coefficients, tx = treatment (0=control, 1=probiotic), $gender$ = patient's gender (0=female, 1=male), age =patient's age at last birthday, $Day7$ = MELD score at Day 7 (0=No, 1=Yes), ..., $Day30$ = MELD score at Day 30 (0=No, 1=Yes). This implies that the baseline MELD score is represented by $Day7=Day14=Day21=Day30=0$. Interpreting this model, which makes maximum use of all available MELD scores, the coefficient β_4 is the estimate of the change in MELD score from baseline to Day 7, β_5 is the estimate of the change in MELD score from baseline to Day 14, etc. By combining all of the information into a single model, we can adjust the MELD score changes for other factors as well as test for a difference in the slopes of the changes between the two treatment groups. The model can, of course, be extended beyond 30 days if measures are available. The fit of the model will be assessed primarily through the likelihood ratio test of the fitted model to the intercept only model. All coefficients will be tested for significance at a critical level of $p=0.05$.

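### Moderate trial: making the already planned baseline-adjusted ANCOVA primary, in place of the unadjusted t-test of MELD change, would be a free but modest gain in precision

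*Combined protocol and SAP*

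**What the plan says.** Section 13 of the combined protocol and SAP prints a sample size and an analysis plan for the moderate trial.

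- **Primary analysis:** "Our primary analysis of change in MELD score from baseline to 30 days will be an unadjusted comparison of change". The measure is Day-30 MELD less baseline MELD, and the arms are compared by a t-test that allows for unequal variances, two-sided at 0.05.
- **Secondary analyses:** these are meant to explore factors that influence the change and to correct for imbalances between arms. The first is the adjusted model: "Our initial model will be an Analysis of Covariance (ANCOVA) model with change in MELD score as the outcome". Its predictors are the treatment arm and baseline MELD. Models with further covariates and longitudinal mixed models follow.
- **Sample size:** "an overall sample size of 108 patients (54 in each treatment group) achieves 80% power with an alpha level of 0.05". The target is a 3-point difference between arms (8.0 under probiotic, 5.0 under control), and the assumed SD, the same in both arms, is 5.559. The next paragraph expects a multivariate model to be able to detect smaller treatment differences.

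No reason is given for keeping the unadjusted test primary. The three MELD randomisation strata in section 3 belong to the severe trial. No stratification by baseline MELD is described within the moderate trial.

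**The concern.** Subtracting baseline is not the same as adjusting for it. A change score fixes the slope of Day-30 MELD on baseline MELD at 1, whereas ANCOVA estimates the slope. Under randomisation both target the same treatment effect. ANCOVA costs one degree of freedom and otherwise has variance no larger in large samples. If the true slope is below 1, an arm that by chance starts with higher MELD will tend to fall further whatever its treatment, and the change-score estimate carries that difference.

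The plan recognises both benefits of adjustment (balance and power) but takes its confirmatory p-value from the analysis that has neither. If the two analyses disagree, the less precise one decides.

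**Working it through.** **Inputs from section 13.** Difference 8.0 − 5.0 = 3.0 MELD points; SD 5.559; 54 evaluable per arm; two-sided alpha 0.05; baseline mean 17.0 ("change in MELD score from baseline (mean=17.0) to 30 days"). From section 3: moderate disease means MELD ≤ 20.

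**Assumptions.** The text calls 5.559 the SD of the MELD score but uses it in a test of change, so I take it as the SD of change. The baseline SD (s) and the slope of Day-30 on baseline MELD (b) are not given, so I use a range for each.

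**Step 1: reproduce the plan's figure.** Standardised difference = 3/5.559 = 0.540. The normal approximation gives 54 per arm and 80.1% power. The exact noncentral t gives 79.4% at 54 per arm and 80.1% at 55. Inflation for 20% loss: 54/0.80 = 67.5, so 68 per arm and 136 in total. The stated figures reproduce.

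**Step 2: how large can the baseline SD be?** For a variable with mean 17 and ceiling 20, the largest possible SD is √[(20 − 17)(17 − minimum)], reached only if every patient sits at one extreme or the other:

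- minimum 14: √(3 × 3) = 3.0
- minimum 10: √(3 × 7) = 4.6
- minimum 8: √(3 × 9) = 5.2

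A baseline SD of 5.559 would need a minimum near 17 − 5.559²/3 = 6.7 and nobody between the extremes. Day-30 MELD has no such cap. I therefore use s = 2 to 3.

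**Step 3: ANCOVA power.** Var(change) = residual variance + (1 − b)²s², so the ANCOVA residual variance is 5.559² − (1 − b)²s² = 30.90 − (1 − b)²s². For example, s = 3 and b = 0.3 give 30.90 − 0.49 × 9 = 26.49, a residual SD of 5.147. Power is by noncentral t with 54 per arm and one degree of freedom fewer than the t-test:

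| Baseline SD | b = 0.3 | b = 0.5 | b = 0.7 | b = 1 |
|---|---|---|---|---|
| 2 | 81.9% | 80.6% | 79.8% | 79.3% |
| 3 | 85.1% | 82.3% | 80.4% | 79.3% |

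The comparator is 79.4% for the t-test, so the gain runs from nil to about 6 percentage points.

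**Step 4: shift from chance imbalance.** SE of the baseline difference = s√(2/54): 0.38 for s = 2 and 0.58 for s = 3. The change-score estimate moves by (1 − b) × imbalance, in the opposite direction to the imbalance. At b = 0.5:

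- one-SE imbalance: 0.19 to 0.29 points, which is 6% to 10% of 3.0
- 1.96-SE imbalance (0.75 to 1.13 points): 0.38 to 0.57 points

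**The case against.** **It is not an error.** The t-test holds alpha at 0.05 and is unbiased over randomisation, and the sample size was computed for that test. A reader might infer that the design is underpowered or its primary estimate biased. The documents support neither: the planned power is kept, and the shift in Step 4 is conditional on the imbalance that happens to occur. This part of the objection stands in full.

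**The gain can be made to look much larger.** If baseline and Day-30 SDs are taken as equal, ANCOVA variance is (1 + ρ)/2 of the change-score variance, where ρ is the correlation between the two measurements. Power at 54 per arm is then 93.1%, 89.4% and 85.4% at ρ = 0.3, 0.5 and 0.7. With a baseline SD of 5.559, a one-SE imbalance of 1.07 points would move the estimate by 0.53 points at ρ = 0.5, or 18% of the target. A reader might infer gains of that size. With 5.559 as the SD of change, equal SDs imply a baseline SD of 5.559/√[2(1 − ρ)], which is 4.70, 5.56 and 7.18 at those correlations. A MELD ceiling of 20 with mean 17.0 makes such values implausible.

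**The plan already contains the ANCOVA.** It is the first secondary model and is there to deal with imbalance. That limits the harm, since the adjusted result will be seen, but it does not make that result the basis of the conclusion.

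**The moderate trial has its own application.** Section 3 says so, and this protocol's arms and its inclusion criterion g concern severe disease. The application is not available here and may order the analyses differently. That limits what can be settled here, but the moderate trial's sample size and analysis plan are printed in section 13 and can be corrected there.

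**Conclusion.** The point holds as a free improvement. The plan's primary analysis of the moderate trial gives up some precision, and protection against chance imbalance in baseline MELD, that an analysis it already specifies would supply. With 5.559 as the SD of change, baseline SD 2 to 3 and slope 0.3 to 0.7 (the last two assumed), ANCOVA has about 80% to 85% power against 79.4%. At slope 1 there is nothing to gain, and the cost is one degree of freedom.

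The direction is secure: across this range ANCOVA is essentially equal or better. The size is not, because the documents report neither the baseline SD nor the slope. The severe trial's log-rank analysis of 6-month mortality is not affected.

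**What to change.** In the moderate trial's analysis plan in section 13, reverse the order of the two analyses:

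- **Primary:** ANCOVA of Day-30 MELD (or change; the treatment estimate is the same) on treatment and baseline MELD, two-sided 0.05, with heteroscedasticity-robust standard errors so that the present allowance for unequal variances is kept.
- **Sensitivity:** the unadjusted t-test of change as now written.
- **Sample size:** unchanged. Sized for the t-test, it is adequate or slightly conservative for ANCOVA.

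Make the same change in the separate application for the moderate trial, before any unblinded look at outcomes. The cost is wording in two documents, with no new data, visits or patients.
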